3.6 Analysis of Exposure-Response

Exposure-response analyses will be performed to propose target concentrations using PK parameters estimated by population-PK, efficacy variables, and biomarker, which will be described in a separate analysis plan.

3.7 Safety Assessment

The Safety Population will be used for all safety analyses. Safety will be summarized descriptively by treatment group.

Descriptive summary statistics will be provided for all safety variables, including 12-lead ECGs, vital signs, clinical laboratory assessments, and AEs reported during the study.

3.7.1 Adverse Events

AEs will be monitored and documented from the time informed consent is obtained until Week 28. All AEs will be coded using MedDRA v24.0.

Treatment-emergent AEs (TEAEs) are defined as AEs that start on or after the first dose of study drug.

Events of serious hypersensitivity that are Grade 3 or higher or lead to treatment study drug discontinuation and vacuolization associated with immunoglobulin will be monitored as AESIs.

An overview of AEs will be provided including counts and percentages of patients (and event counts) with the following:

- Any TEAEs
- Any Grade 3 or higher TEAEs
- Any study drug related TEAEs
- Any study drug related Grade 3 or higher TEAEs
- Any AEs related to anti-CMV rescue medication
- Any AESIs
- Any Grade 3 or higher AESIs
- Any SAEs
- Any treatment-emergent serious AEs (TESAEs)
- Any TEAEs leading to discontinuation of study drug
- Any TEAEs leading to discontinuation of study
- Any AEs leading to death
- Any AEs related to COVID-19

Numbers and percentages of patients will also be presented by SOC and PT for each category in the summary tables.

Listings will be presented for AEs, Grade 3 or higher AEs, SAEs and TEAEs leading to discontinuation of study drug.

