At the 100 mg/kg dose, reversible hematologic changes were observed at the end of the 4-week dosing period (a decreased erythrocyte count, hematocrit value, and hemoglobin concentration in 3 of 12 animals, with an increased reticulocyte ratio in 2 of these animals). The increased or normal reticulocyte ratio and unchanged leukocyte counts in these animals suggested there were minimal toxicological effects on hematopoiesis. The possibility that NPC-21 had some effects on peripheral erythrocytes cannot be excluded. Thus, the no observed adverse effect level was considered to be 50 mg/kg in both male and female monkeys.

A first-in-human Phase 1 study of NPC-21 was conducted in 40 healthy Japanese and Caucasian male adults, in which a single administration of NPC-21 or placebo was infused over a duration of 60 minutes. This single ascending dose study confirmed tolerability of NPC-21 up to 20 mg/kg. All adverse events were mild in severity. There were no SAEs, deaths, significant adverse events, or adverse events that led to treatment discontinuation. Anti-NPC-21 antibodies were detected in 6 out of 40 individuals, but in all cases, the antibodies were present prior to administration of NPC-21.

In the Phase 1 study, the maximum serum concentration, area under the concentration-time curve (AUC) from time 0 to the last measurable concentration, and the AUC from time 0 to infinity increased dose-dependently as was demonstrated by a linear regression analysis and a power model analysis. For other pharmacokinetic parameters (time to maximum serum concentration, half-life [t_{1/2}], clearance, volume of distribution, mean residence time, and elimination rate constant), no significant difference between dose levels was observed. The t_{1/2} was estimated to be 612.30 to 790.41 hours, and the elimination pattern was considered biphasic.

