3 STUDY DESCRIPTION

3.1 Summary of Study Design

This is a Phase 2, randomized, double-blind, placebo-controlled study of NPC-21 for kidney transplant recipients at high risk of CMV infection at approximately 25 clinical sites in the United States and Japan. Approximately 108 eligible patients will be randomized in a 4:1:4 ratio prior to first study drug administration to receive 6 mg/kg NPC-21, 12 mg/kg NPC-21, or placebo. Randomization will be stratified by region (United States or Japan).

Figure 1 displays a schematic of the study's design.

Figure 1. Study Schematic

*When the patient meets the primary endpoint, the patient moves to the rescue phase

Adult CMV seronegative patients receiving a first kidney transplant from CMV seropositive donors will be enrolled in the study. Participation in the study will consist of a Screening Period (up to 14 days prior to first study drug administration), a 16-week Treatment Period, and a 12-week Observation Period. The total duration of the study (including Screening, Treatment Period, and Observation Period) will be approximately 30 weeks. After first study drug administration, patients who develop detectable CMV disease (CMV syndrome or tissue-invasive CMV disease) or CMV viremia (defined as the detection of ≥ 250 IU/mL in plasma measured by polymerase chain reaction [PCR] analysis in central laboratory or meets the local criteria for CMV viremia measured by PCR analysis or antigenemia testing) can enter the Rescue Phase of the study and be treated by anti-CMV agents per local standard of care until the patient is negative for CMV viremia, has recovered from CMV disease, or up to Week 28, whichever comes first. When this rescue therapy is completed, the Rescue Phase is terminated at least 4 Study Weeks after the last study drug administration and all Week 28 procedures will be performed as per Section 6.7 Early Termination Visit and Withdrawal Procedures.

The 16-week Treatment Period will include study drug administration on Day 1 and at Weeks 4, 8, and 12. The 16-week Treatment Period will begin as soon as practical post-transplant but no later than 7 days post-transplant.

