9 SAFETY ASSESSMENTS

9.1 Adverse Events

An adverse event is defined as any untoward medical occurrence in a clinical investigation patient administered a pharmaceutical product, which does not necessarily have a causal relationship with this treatment. An adverse event can therefore be any unfavorable and/or unintended sign (including an abnormal laboratory finding), symptom, or disease temporally associated with the use of an investigational medicinal product, whether or not related to the investigational medicinal product. All adverse events, including observed or volunteered problems, complaints, or symptoms, are to be recorded on the appropriate eCRF.

Adverse events, which include clinical laboratory test variables, will be monitored and documented from the time informed consent is obtained until Week 28. Should the patient terminate the study early, SAEs should be reported up until the Early Termination visit or 90 days after the last administration of study drug, whichever is later. Patients should be instructed to report any adverse event that they experience to the Investigator, whether or not they think the event is due to study drug. Beginning at the time informed consent is obtained, Investigators should make an assessment for adverse events at each visit and record the event on the appropriate adverse event eCRF.

Wherever possible, a specific disease or syndrome rather than individual associated signs and symptoms should be identified by the Investigator and recorded on the eCRF. However, if an observed or reported sign or symptom is not considered a component of a specific disease or syndrome by the Investigator, it should be recorded as a separate adverse event on the eCRF. Additionally, the condition that led to a medical or surgical procedure (eg, surgery, endoscopy, tooth extraction, or transfusion) should be recorded as an adverse event, not the procedure itself.

Any medical condition already present at the time of signing informed consent should be recorded as medical history and not be reported as an adverse event unless the medical condition or signs or symptoms present at Baseline changes in severity, frequency, or seriousness at any time during the study. In this case, it should be reported as an adverse event.

Laboratory Abnormalities

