- a. Screening procedures will take place up to 14 days prior to first study drug administration.
- b. The Treatment Period will begin as soon as practical post-transplant but no later than 7 days post-transplant.
- c. During the Treatment Period, visits on dosing days (Day 1 and at Weeks 4, 8, and 12) should be conducted in person. Visits on non-dosing days of the Treatment Period (Weeks 1, 2, 3, 5, 6, 7, 9, 10, 11, 13, 14, 15, and 16) may be conducted by home healthcare services (United States only). Home healthcare services may perform the following procedures at non-dosing day visits: record concomitant medications, obtain body weight, perform physical examination, record vital signs, collect samples for analysis by the central laboratory, perform 12-lead ECG, perform EQ-5D-5L, and record adverse events.
- d. After first study drug administration, patients who develop detectable CMV disease (CMV syndrome or tissue-invasive CMV disease) or CMV viremia (defined as the detection of ≥250 IU/mL in plasma measured by PCR analysis in central laboratory or meets the local criteria for CMV viremia measured by PCR analysis or antigenemia

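### The TEAE definition has no worsening clause, so an adverse event that begins between consent and first dose and worsens on study drug can be missing from the TEAE summaries

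*SAP*

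**What the plan says.** SAP 3.7.1 gives the only definition of a treatment-emergent event: "Treatment-emergent AEs (TEAEs) are defined as AEs that start on or after the first dose of study drug". Protocol 10.2.4 uses the term without defining it, so the SAP sentence governs.

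Collection begins earlier than that. SAP 3.7.1 states that "AEs will be monitored and documented from the time informed consent is obtained until Week 28", in line with Protocol 9.1. Appendix A of the protocol adds that "Screening procedures will take place up to 14 days prior to first study drug administration", and Protocol 3.1 that "The 16-week Treatment Period will begin as soon as practical post-transplant but no later than 7 days post-transplant". Inclusion criterion 2 admits patients who are still awaiting the transplant as well as those who have had it within the preceding 7 days.

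Protocol 9.1 has a rule for worsening, but it concerns conditions that predate consent. The starting point is this: "Any medical condition already present at the time of signing informed consent should be recorded as medical history". The exception to it reads: "unless the medical condition or signs or symptoms present at Baseline changes in severity, frequency, or seriousness at any time during the study". Such a change makes the condition reportable. The laboratory paragraph of the same section makes clinically significant findings reportable if they are detected during the study, or if they were present at consent and then worsen significantly.

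**The concern.** Kidney transplantation and the start of immunosuppression can fall between consent and Day 1, so some patients will have adverse events already open when study drug starts. If such an event becomes more severe after dosing, a definition based on start date alone does not recognise the change.

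Safety is part of the primary objective. Haematology is the area that Protocol section 1 singles out for careful monitoring, because the monkey study showed "a decreased erythrocyte count, hematocrit value, and hemoglobin concentration in 3 of 12 animals". Anaemia is also an obvious example of an event that could begin around surgery, before the first dose. The TEAE tables by system organ class and preferred term are where a reader would look first for an imbalance between arms.

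**Working it through.** The documents give no figure to reproduce. The check is to follow four kinds of event through the rules.

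| Event | Rule that applies | Counted as a TEAE? |
|---|---|---|
| Starts on or after first dose | SAP 3.7.1 | Yes |
| Start date missing or partial, and a pre-dose start or end cannot be established | SAP 3.1.5, worst case | Yes |
| Condition or laboratory finding present at consent, worsens after first dose | Protocol 9.1: the worsening is reported as an AE | Yes, if the worsening date is entered as the start date; the documents do not say which date to enter |
| AE with known onset between consent and first dose, worsens in grade after first dose | None | No, unless the site opens a new record |

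Two features follow.

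1. *Dependence on the date of consent.* Take post-operative anaemia that goes from Grade 1 to Grade 3 after Day 1. If the patient consented after surgery with the anaemia already present, it is medical history and its worsening is a new AE that can be a TEAE. If the patient consented before surgery, it is an open AE with a pre-dose start and is not a TEAE. The clinical course is the same and the count differs.

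2. *Uneven conservatism.* An event with an uncertain date is taken as treatment-emergent. An event with a known pre-dose onset that demonstrably worsens on study drug is not.

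Where the event is lost: the AE overview in SAP 3.7.1 has 13 rows, and 7 of them are restricted to treatment-emergent events. These are any, Grade 3 or higher, drug-related, drug-related Grade 3 or higher, serious, leading to discontinuation of study drug, and leading to discontinuation of the study. No row counts all AEs or all Grade 3 or higher AEs regardless of timing. A non-serious worsening of the fourth kind, outside the special categories, therefore appears in no overview row.

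Where it is still visible:
- The rows for SAEs, AESIs and deaths are not limited to TEAEs, nor are the listings of AEs, Grade 3 or higher AEs and SAEs. An event that turns serious after dosing is counted with pre-dose SAEs but not among the treatment-emergent ones.
- SAP 3.7.2 summarises change from baseline, with minimum and maximum post-treatment values, for selected parameters. It also cross-tabulates baseline grade against worst post-baseline CTCAE grade for selected tests, and gives a Low/Normal/High shift for all parameters. Baseline is the last value before first dose (SAP 3.1.3), so a post-surgical haemoglobin is the comparator.
- Two limits remain. The selected tests are not named. A patient who is Low at baseline and lower afterwards stays in the Low-to-Low cell.

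Size, on assumed inputs only. Suppose 30% to 60% of patients have an AE with onset after consent that is still open at first dose, and 10% of those worsen in grade without a new record.
- Lower: 0.30 × 0.10 = 3%; 0.03 × 48 = 1.4 patients per main arm.
- Upper: 0.60 × 0.10 = 6%; 0.06 × 48 = 2.9 patients per main arm.

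Effect on a contrast, again assumed. Let true worsening on study drug be 30% against 15% with 48 patients per arm, and let a share q of the affected patients in each arm have pre-dose onset and no new record. The visible difference is 15 × (1 − q) percentage points.

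| q | Counted, 48 per arm | Visible difference (points) |
|---|---|---|
| 0 | 14.4 vs 7.2 | 15 |
| 0.25 | 10.8 vs 5.4 | 11.3 |
| 0.50 | 7.2 vs 3.6 | 7.5 |
| 0.75 | 3.6 vs 1.8 | 3.8 |

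The documents give neither q nor any AE rate.

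**The case against.** The best case for leaving the plan alone has four parts.

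First, a reader might infer that peri-transplant events that worsen on study drug are never treatment-emergent. The documents do not support that. Patients may enrol after surgery, and Protocol 9.1 makes the worsening of anything present at consent reportable, with nothing to prevent a post-dose start date. The gap is confined to onset between consent and first dose, a window of about 14 days at most. The word Baseline in the protocol's exception might seem to extend the rule to Day 1. Its subject, however, is a condition present at consent, and it does not say that an AE already open must be re-recorded. This part of the objection narrows the point but does not remove it.

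Second, neither document says that a worsening event keeps its original start date, and eCRF completion instructions are not in the text reviewed. That is correct: a site may open a new record. Nothing requires it to, so the classification is left to site practice.

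Third, a reader might infer that a haematology signal would be hidden. That also goes too far. The laboratory summaries do not depend on TEAE status and show part of any worsening. The animal changes were reversible, were seen at 100 mg/kg, and are described as having sufficient safety margins. What stands is that the grade shift is not committed to haematology, and that laboratory tables carry neither causality nor discontinuation.

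Fourth, the safety analysis is descriptive, and no efficacy test or stated stopping criterion depends on the TEAE count. This limits the consequence to how the safety profile is described.

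**Conclusion.** The point holds in a limited form. An AE with known onset between consent and first dose that worsens in grade on study drug is not a TEAE under SAP 3.7.1, and no rule requires a new record that would make it one. The treatment-emergent rows and their system organ class and preferred term tables can therefore undercount worsening on study drug, and identical courses can be classified differently according to when consent was signed.

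The undercount is partial: serious, special-interest and fatal events, the listings, and the laboratory summaries show some of what the TEAE counts miss. Its size cannot be derived from the documents. The 1 to 3 patients of 48 per main arm rests entirely on the assumed 30% to 60% and 10%, and on no new record being opened.

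**What to change.** Define a TEAE as an AE that starts, or worsens in CTCAE grade, on or after the first dose of study drug, and state that the date of worsening is used to classify such an event.

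Timing limits how this can be done. SAP version 1.0 was finalised on 29 March 2023 and the database was locked on 30 March 2023, so a note to sites on eCRF completion can help only later studies. For this trial:

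- Keep the planned TEAE tables and add, through an SAP addendum, a supplementary AE table under the wider definition, labelled as specified after lock. The sponsor has already documented post-lock changes this way, in the addendum of 15 May 2023. The table can include only events whose change in grade was captured; state how many events open at first dose lack that information.
- Name haemoglobin and the other gradable haematology parameters in the CTCAE shift table of SAP 3.7.2. Abnormal laboratory results are already to be graded, so no new data are needed.

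The cost is one sentence of definition, one extra table and a short parameter list. The downside is slightly higher TEAE counts in all arms. It is a cheap improvement.

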3.7.2 Clinical Laboratory Evaluations

Standard clinical laboratory profiles for blood biochemistry, hematology, coagulation, and urinalysis will be evaluated at the local laboratory at Screening and at the local laboratory (Japan sites) and central laboratory (US sites) prior to study drug administration on dosing days (Day 1 and at Weeks 4, 8, and 12) and at Weeks 1, 2, 6, 10, 14, 16, 20, 24, and 28. Samples for evaluation by the central laboratory may be collected by home healthcare services at non-dosing day visits. See Appendix B of the protocol for a complete list of laboratory analytes.

Clinical laboratory evaluations will be summarized using descriptive statistics if sufficient data is available for selected laboratory parameters including absolute measurements and changes from baseline by scheduled time of evaluation. Changes from baseline by scheduled time of evaluation will include last analysis visit, maximum post-treatment value, and minimum post-treatment value. Both scheduled and unscheduled post-treatment visits will be considered for the summaries of the maximum and minimum post-treatment values.

Abnormal laboratory results will be graded according to NCI CTCAE v5.0. A shift table, presenting the 2-way frequency tabulation for baseline and the worst post-baseline grade according to NCI CTCAE grades, will be provided for selected clinical laboratory tests. For select parameters (e.g. glucose), separate shift tables indicating hyper-and hypo-directionality of change may be produced. The worst post-baseline grade will be derived from all post-baseline visits including scheduled and unscheduled.

The shift table for all parameters will be provided based on the categories Low, Normal and High based on normal ranges. Hyper-and hypo-directionality of change may be produced.

Clinical laboratory evaluations will be listed by-patient. Abnormal values will be flagged.

3.7.3 Vital Signs

Vital signs (systolic and diastolic blood pressure, pulse rate, and body temperature) will be taken in the supine or sitting position after resting at Screening; prior to study drug administration on dosing days (Day 1 and at Weeks 4, 8, and 12); within 1 hour of the end of the infusion on Day 1; and at Weeks 1, 2, 3, 5, 6, 7, 9, 10, 11, 13, 14, 15, 16, 17, 18, 19, 20, 21, 22, 23, 24, 26, and 28. Vital signs may be taken by home healthcare services at non-dosing day visits.

Descriptive statistics will be provided for vital signs assessments. Changes from baseline by scheduled evaluation, and maximum and minimum post-treatment values may be presented. Both scheduled and unscheduled post-treatment values will be considered for summaries of the minimum and maximum.

The counts and percentages of patients with the following potentially abnormal vital signs at any post-baseline visits will be summarized:

- Pulse rate < 50 bpm and decrease \geq 15 bpm from baseline
- Pulse rate > 100 bpm and increase \geq 15 bpm from baseline
- Systolic blood pressure \leq 90 mmHg and decrease \geq 20 mmHg from baseline
- Systolic blood pressure \geq 140 mmHg and increase \geq 20 mmHg from baseline
- Diastolic blood pressure \leq 50 mmHg and decrease \geq 10 mmHg from baseline
- Diastolic blood pressure \geq 90 mmHg and increase \geq 10 mmHg from baseline

Vital signs assessments will be listed by-patient.

3.7.4 *Electrocardiograms*

A 12-lead ECG will be performed in a supine position after resting at Screening; prior to study drug administration at Weeks 4, 8, and 12; and at Weeks 16, 20, 24, and 28. Additional follow-up ECGs may be performed if clinically indicated. A 12-lead ECG may be performed by home healthcare services at non-dosing day visits.

Overall evaluation of ECG is collected at each visit in terms of

- Normal
- Abnormal, not clinically significant
- Abnormal, clinically significant

The counts and percentages of patients within each category will be summarized by treatment group and visit.

ECG assessments will be presented in a by-patient listing.

3.7.5 *Physical Examinations*

A complete physical examination will be performed at Screening; prior to study drug administration on dosing days (Day 1 and at Weeks 4, 8, and 12); within 1 hour of the end of the infusion on Day 1; at Weeks 1, 2, 3, 16, 20, 24, and 28; and at the initiation of the Rescue Phase. A physical examination may be performed by home healthcare services at non-dosing day visits.

The physical examination will be presented in a by-patient listing.

3.7.6 *Data Safety Monitoring Board*

The Data Safety Monitoring Board (DSMB) will meet to review unblinded aggregate and individual patient data related to safety, data integrity, and overall conduct of the study and will provide recommendations to continue, temporarily halt, modify, or terminate the study based on data analysis. The committee may communicate other recommendations or concerns as deemed appropriate. Additional information will be provided in the DSMB charter as approved by the members.

3.8 **Interim Analysis**

No interim analysis is planned.

4 **CHANGES FROM PROTOCOL-SPECIFIED STATISTICAL ANALYSES**

In Section 3.4.2.2 for secondary efficacy analysis, the below secondary analysis was added compared to protocol:

- Duration of the detection of CMV DNA ≥ 250 IU/mL in plasma measured by PCR analysis in central laboratory.

The section 3.4.3 was added as the exploratory analysis to the endpoints.

5 **PROGRAMMING SPECIFICATIONS**

Analyses will be performed using SAS® version 9.3 or higher. All available data will be presented in patient data listings which will be sorted by patient and visit date as applicable. Detailed Programming Specifications will be provided in a separate document.

STATISTICAL ANALYSIS PLAN ADDENDUM

Protocol Title: A Phase 2, Randomized, Double-Blind, Placebo-Controlled Study of NPC-21 for Kidney Transplant Recipients at High-Risk of Cytomegalovirus Infection (LionHeart21)

Protocol Number: NPC-21-2

Protocol Version/Date: Version 5.0/18 October 2021

Investigational Product: NPC-21

Sponsor: Nobelpharma Co., Ltd.
[name]
[name]
[contact]
[contact]

SAP Version/Date: Version 1.0/29 March 2023

SAP Addendum Version/Date: Version 1.0/15 May 2023

CONFIDENTIAL

